### 1.5 Known and Potential Benefits and Risks to Patients

Complete information may be found in the IB provided to each investigator. Each investigator must become familiar with all information in the IB before commencing this study.

The potential benefits to participating patients with acute postsurgical pain following abdominoplasty are (1) that they may experience a reduction in acute postoperative pain as a result of treatment with INL-001, (2) that they will understand they are contributing to the scientific knowledge that may lead to expansion of the treatment options for patients' acute postsurgical pain, and (3) because INL-001 is implanted (not injected) into the surgical site, accidental intravascular injection/surgical site infiltration that often leads to bupivacaine's most serious potential central nervous system (CNS) and CV systemic toxicities may be prevented.

The potential risks of study participation include those associated with exposure to INL-001 per the FDA-approved labeling and the risks of medical evaluation, including venipuncture and other risks associated with the required medical procedures.

Because individual patient factors may impact the safety of an amide local anesthetic such as bupivacaine, there is a potential risk for severe life-threatening adverse effects associated with the local administration of bupivacaine. Therefore, INL-001 should be administered in a setting where trained personnel and equipment are available to promptly treat patients who show evidence of CNS or CV toxicity. Monitoring cardiovascular and neurologic status, as well as vital signs, should be performed during and after placement of INL-001.

Allergic-type reactions are rare and may occur as a result of sensitivity to bupivacaine or to other formulation ingredients. These reactions are characterized by signs of urticaria, pruritus, erythema, angioedema (including laryngeal edema), tachycardia, sneezing, nausea, vomiting, dizziness, syncope, excessive sweating, elevated temperature, and possibly anaphylactoid-like symptoms (including severe hypotension). Cross-sensitivity among members of the amide-type local anesthetic group has been reported.

Innocoll

Clinical Study Protocol With Amendment 02

Study INN-CB-024

Controlled Study-Postsurgical Analgesia

---

## **2 STUDY OBJECTIVES**

The primary objective of the study is to evaluate the analgesic effect of treatment (ie, efficacy) with INL-001 implants compared with placebo implants after placement into the surgical site during abdominoplasty.

The secondary objective is to assess the safety and tolerability of INL-001 implants after placement in the surgical site during abdominoplasty.

Innocoll

Clinical Study Protocol With Amendment 02

Study INN-CB-024

Controlled Study-Postsurgical Analgesia

### **3 STUDY DESIGN**

#### **3.1 General Study Design**

This is a multicenter, randomized, double-blind, placebo-controlled efficacy and safety study of the INL-001 (bupivacaine HCl) implant, at 300 mg, in patients following abdominoplasty. On the day of surgery (study day 1), eligible patients will be randomly assigned to treatment in a 1:1 ratio to receive either INL-001 (three 100-mg implants containing a total dose of 300 mg of bupivacaine HCl) or 3 placebo collagen implants. Patients will then undergo abdominoplasty under general anesthesia and have INL-001 or placebo implanted intraoperatively.

The duration of study participation for each patient will be a maximum of 75 ( $\pm 3$ ) days, consisting of a screening period (up to 45 days before surgery), an inpatient period (preoperative, intraoperative, immediately postoperative) of approximately 4 days, and an outpatient follow-up period (up to 30 days [ $\pm 3$  days] after treatment) including an end-of-study visit. Efficacy assessments will be made through 72 hours after treatment (after implant placement). Posttreatment (time measured from Time 0 [placement of first implant]) safety assessments will be made throughout the study after the informed consent form (ICF) is signed, and as specifically scheduled through 72 hours posttreatment, on day 7 ( $\pm 1$  day) (telephone), on day 15 ( $\pm 3$  days) (clinic visit), and on day 30 ( $\pm 3$  days) (clinic visit). Unless the investigator determines further hospitalization is necessary, the patient will be discharged on the day occurring 72 hours (day 4) after surgery.

During the screening period, all patients will provide informed consent and undergo eligibility and other screening and safety assessments (medical history including review of prior medications, physical examination, urine drug screen, serum pregnancy test for women of childbearing potential, clinical laboratory tests [hematology, chemistry, urinalysis], vital signs measurement, and 12-lead electrocardiography [ECG]). Vital signs include body temperature, pulse, systolic and diastolic blood pressure, respiration rate, and oxygen saturation measured by pulse oximetry. The reason(s) a patient does not meet screening criteria will be recorded, if applicable. Recording of adverse events and concomitant medication use will commence once a patient signs the ICF.

On the day of surgery (day 1), patient eligibility will be reconfirmed before the start of surgery (including medical history, urine drug screen, urine pregnancy test for women of childbearing potential, vital signs), patients will be randomly assigned to treatment with study drug (INL-001 or placebo collagen implant), and adverse events and prior/concomitant medications will be reviewed.

Patients will undergo an abdominoplasty with rectus sheath plication using standard surgical procedures conducted under general anesthesia (see anesthesia protocol below in [Section 5.1.1](#)), with no other local anesthetic used at the surgical site. All patients should undergo an abdominoplasty procedure with an incision that does not extend above the umbilicus. The approach should be anterior. The incision should in general be from one anterior superior iliac spine (ASIS) to the other. The exact incision length may vary depending on the patient's anatomy and the desired cosmetic outcome. All packs/gauze should be removed and adequate hemostasis must be achieved prior to skin closure. Surgical drains should be placed at the discretion of the surgeon and their use recorded. Ancillary procedures (eg, liposuction, breast augmentation/reduction) are prohibited.

Innocoll

Clinical Study Protocol With Amendment 02

Study INN-CB-024

Controlled Study-Postsurgical Analgesia

Placement of study drug is detailed below in [Section 5.1.2](#). The time of the first placement of study drug (placement of first implant) is considered Time 0 and will be recorded. Use of analgesic and all medications during surgery will be recorded. At the surgeon's discretion, if a significant surgical/medical complication is encountered during surgery, study drug will not be implanted and the patient will be considered enrolled but not treated.

After surgery, patients will be transferred to a postanesthesia care unit (PACU) or other postoperative recovery area for monitored observation. The times patients enter and are discharged from the PACU will be recorded to calculate time to discharge from the PACU. Patients will be monitored with pulse oximetry starting in the PACU through 24 hours posttreatment. After leaving the PACU (time in PACU to be at the discretion of the investigator), patients will be placed in the postoperative unit or clinical research unit for domiciled observation. Vital signs, including body temperature, pulse, systolic and diastolic blood pressure, respiration rate, and oxygen saturation measured by pulse oximetry, will be assessed at multiple time points through discharge, and in the clinic on days 15 and 30; 12-lead ECG will be done on day 30.

Adverse event and concomitant medication information, including use of rescue medication, will be collected throughout the study (inpatient and outpatient). Surgical wound healing assessments will be made at 24, 48, and 72 hours after Time 0 and on days 7, 15, and 30 using the specified list and assessed for and recorded as adverse events as appropriate. The Southampton Wound Grading System will also be completed 72 hours posttreatment/prior to discharge ( $\pm 4$  hours) and on days 15 and 30. Assessment for signs and symptoms potentially indicative of systemic bupivacaine toxicity will be made after Time 0 at the following time points: 0.5, 1, 2, 3, and 4 hours (each  $\pm 15$  minutes), and 5, 7, 9, 12, 15, 18, 24, 48, and 72 hours (each  $\pm 1$  hour), and days 7 ( $\pm 1$  day) and 15 ( $\pm 3$  days) using the specified list and assessment made and recorded as adverse events as appropriate.

At any time that a patient is determined to have systemic bupivacaine toxicity, a bupivacaine blood sample will be collected and 12-lead ECG will be performed. Systemic bupivacaine toxicity will be recorded as an adverse event. The patient may be treated at the discretion of the investigator, including obtaining repeat bupivacaine blood levels, 12-lead ECG, or removal of the implants.

After surgery, patient reports of pain intensity using an 11-point numeric pain rating scale (NPRS) will be recorded at multiple time points through 72 hours posttreatment. Scheduled pain intensity scores will be recorded after Time 0 at 0.5, 1, 2, 3, 4, 5, 6, 8, 10, 12, 18, 20, 24, 28, 32, 36, 48, and 72 hours. Each assessment prior to hour 10 has a  $\pm 15$ -minute window; each assessment after and including hour 10 has a  $\pm 30$ -minute window. The 0.5-hour and 1-hour NPRS assessments may be omitted if, on the basis of clinical judgement, the patient is not yet awake and alert enough to appropriately answer the NPRS after surgery. Pain intensity assessments scheduled between 2400 (midnight) and 0600 (6 am) may be limited to collection every 4 hours if the patient is sleeping. However, consecutive pain assessments may not be missed, and the hour 12, 24, 48, and 72 posttreatment pain assessments must be completed even if they fall between 2400 (midnight) and 0600 (6 am). A pain intensity score will also be collected before **any** rescue pain medication use.

Patients will be permitted rescue medication to manage breakthrough pain when it occurs. Oral acetaminophen at 1000 mg every 4-6 hours as needed for pain (maximum daily dosage 3000 mg)

Innocoll

Clinical Study Protocol With Amendment 02  
Study INN-CB-024

Controlled Study-Postsurgical Analgesia

and/or oxycodone 5-mg tablet(s) may be given (not to exceed 10 mg in a 4-hour period during the inpatient stay). Immediately prior to receiving **any** rescue medication, a pain intensity score must be recorded. If the NPRS score is 4 or less, patients will be discouraged from taking opioid rescue medication; however, rescue medication may be requested and provided at any time. If patients require opioid rescue medication, but are unable to take oral medications, they will be permitted to receive intravenous (iv) morphine (2-3 mg) every 3 hours until they are able to take oral rescue medication. As assessed by the investigator, if a patient's pain is not relieved by oxycodone and/or acetaminophen, the patient is not yet eligible for further treatment with oxycodone and/or acetaminophen, and more than 3 hours have passed since the previous iv morphine dose, a patient may receive a dose of iv morphine (2-3 mg) for pain relief. If the pain remains unrelieved or increases in intensity before additional rescue medication is allowed, additional treatment options will be discussed with the medical monitor.

Following discharge, to report an adverse event, a patient will contact study staff by telephone and report adverse event information, including incidence, duration, and any associated treatment. Patients with pain intensity scores of 4 or more at discharge will be given a written prescription for immediate-release oxycodone at a dosage of 5-10 mg every 4-6 hours as needed as rescue medication for breakthrough pain. Patients prescribed opioid rescue medication will also be permitted to take oral acetaminophen at 1000 mg every 4-6 hours (maximum daily dosage 3000 mg) and/or ibuprofen at 400 mg every 4-6 hours as needed for pain, on an outpatient basis. Patients with pain intensity scores of less than 4 at discharge will be instructed to take oral acetaminophen at 1000 mg every 4-6 hours as needed for pain (maximum daily dosage 3000 mg) and/or ibuprofen at 400 mg every 4-6 hours as needed for pain, on an outpatient basis. Patients who do not receive a written prescription for oxycodone upon discharge will be permitted to request immediate-release oxycodone 5-10 mg if their pain is unrelieved by acetaminophen. Use of opioids, acetaminophen, nonsteroidal anti-inflammatory drugs (NSAIDs), or any other medications after discharge from the hospital will be recorded, with data reviewed by study staff at subsequent contacts.

NOTE: As needed, a patient may receive rescue medication for pain at any time during the inpatient and outpatient portions of the study as described; however, these medications should **not** be taken concomitantly (ie, not at the same time).

A detailed table of procedures and assessments is provided in [Table 1](#).

### **3.2 Planned Number of Patients and Countries**

Up to approximately 432 patients will be screened in order to randomize 372 patients to achieve a minimum of 360 patients randomized and treated [180 evaluable patients per treatment group]). Details about the definition of evaluable patients and sample size are given in [Section 9](#).

The study is expected to start at a time to be determined, with an estimated enrollment period of approximately 6 months, including an interim analysis. Screening to the end of the study for each patient will be approximately 75 ( $\pm 3$ ) days.

Innocoll

Clinical Study Protocol With Amendment 02

Study INN-CB-024

Controlled Study-Postsurgical Analgesia

### **3.3 Justification for Study Design and Selection of Population**

This is a randomized, double-blind, placebo-controlled study designed primarily to assess the efficacy and safety of INL-001 in adult patients scheduled for abdominoplasty. The study design employed in this study has previously been used successfully in 2 clinical Phase 3 studies conducted to demonstrate the efficacy and safety of INL-001 to manage acute postoperative pain in patients undergoing open inguinal hernia repair. The rationale for studying patients undergoing abdominoplasty was previously provided in [Section 1.3](#).

### **3.4 Stopping Rules for the Study**

Innocoll reserves the right to discontinue the study for safety or administrative reasons at any time.

The study will be stopped, until further benefit-risk evaluation is made, if 2 patients require removal of the INL-001 implants due to suspected systemic bupivacaine toxicity as outlined below in [Section 4.3.2](#).

During the conduct of the study, serious adverse events will be reviewed (see [Section 7.1.5](#)), as they are reported from the investigational centers, to identify safety concerns.

The study may also be terminated by the sponsor for any reason at any time. For example, the sponsor could terminate the study in the event of:

- new toxicologic or pharmacologic findings or safety issues from any source (eg, other clinical studies, postmarketing experience) that invalidate the earlier positive benefit-risk assessment
- discontinuation of the development of the investigational medical product

If the entire study is stopped or if elements of the study are stopped, the patients whose participation is terminated early will be monitored according to withdrawal criteria and procedures (see [Section 4.3](#)).

If the study is terminated prematurely, investigator(s) will inform their patients and arrange their appropriate follow-up.

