bupivacaine plasma concentrations will be obtained and the investigator may request that the patient's treatment be unblinded. If the patient received INL-001, the investigator may make the decision to remove the implants as part of the patient's treatment plan for these adverse events. If at all possible, the investigator should discuss the case with the medical monitor before proceeding.

The decision to return a patient to the operating room in order to remove INL-001 implants will be an individualized assessment made on the basis of multiple patient factors (eg, age, comorbidities, hemodynamic status). The determination regarding returning a patient to the operating room for removal of INL-001 implants will be made by the investigator.

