### **5.10 Randomization and Blinding**

Eligible patients will be randomly assigned to treatment in a 1:1 ratio to receive either INL-001 or placebo collagen implants. Patients will not be aware of their treatment allocation and all study staff involved in efficacy and safety assessments will be blinded to treatment assignments until after database lock and release of unblinding randomization codes. Emergency unblinding is allowable if deemed necessary by the investigator, and discussed and agreed with the study medical monitor, for the safety of the patient and will be fully documented and included in protocol deviations. Patients will be stratified by study center and body mass index (BMI) ( $<30 \text{ kg/m}^2$  and  $\geq 30 \text{ kg/m}^2$ ). In the case of a suspected unexpected serious adverse reaction (SUSAR), unblinding of the sponsor will be performed according to the safety management plan.

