#### 7.1.5.3 Reporting a Serious Adverse Event

##### 7.1.5.3.1 Investigator Responsibility

To satisfy regulatory requirements, all serious adverse events that occur during the study, regardless of the assessed relationship to study drug treatment, must be reported to the sponsor by the investigator within 24 hours after the investigator becomes aware of it. Completing the serious adverse event form and reporting the serious adverse event must not be delayed, even if all the information is not available. The investigator does not need to actively monitor patients for adverse events once the study has ended.

The serious adverse event form will be sent to the contract research organization (CRO) and sponsor representatives.

The following information will be provided to record the adverse event accurately and completely:

- study number
- investigator and investigational center identification

Innocoll

Clinical Study Protocol With Amendment 02

Study INN-CB-024

Controlled Study-Postsurgical Analgesia

- patient number
- start date and detailed description of adverse event
- investigator's assessment of the relationship to study drug

Additional information may include:

- age and sex of patient
- date of implantation
- action taken
- outcome, if known
- severity
- explanation of assessment of relationship to study drug
- concomitant medication (including doses, routes of administration, and regimens) and treatment of the event
- pertinent laboratory or other diagnostic test data
- medical history
- results of dechallenge/rechallenge, if known
- for an adverse event resulting in death
  - cause of death (whether or not the death was related to study drug)
  - autopsy findings (if available)

Healing of the surgical wound will be assessed throughout the study and if there is a wound-related event, it will be recorded as such.

Each report of a serious adverse event will be reviewed and evaluated by the investigator and the sponsor to assess the nature of the event and the relationship of the event to the study drug, study procedures, and underlying disease.

Additional information (follow-up) about any serious adverse event unavailable at the time of initial reporting should be provided by the investigator within 24 hours of the time it becomes known.

The investigator must ensure the Institutional Review Board (IRB) is also informed of the event, in accordance with national and local regulations.

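### The only mandatory, counted safety pause (Protocol 3.4) counts implant removals, which 3.1 and 4.3.2 leave to the investigator, so grade 4 bupivacaine toxicity managed without removal does not advance it

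*Protocol*

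**What the plan says.** Protocol section 3.4 gives the sponsor a general right to stop at any time and provides for serious adverse events to be reviewed as they arrive. It has one trigger with a number and a compulsory consequence: the study is halted pending a benefit-risk evaluation "if 2 patients require removal of the INL-001 implants due to suspected systemic bupivacaine toxicity". For that trigger it refers to section 4.3.2.

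Neither section that deals with removal makes it compulsory:

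- Section 3.1, on a patient determined to have systemic bupivacaine toxicity: "The patient may be treated at the discretion of the investigator, including obtaining repeat bupivacaine blood levels, 12-lead ECG, or removal of the implants".
- Section 4.3.2, after a listed grade 4 event: plasma concentrations are obtained, the investigator may ask for unblinding, and if the patient had INL-001 "the investigator may make the decision to remove the implants". Returning the patient to the operating room "will be an individualized assessment made on the basis of multiple patient factors (eg, age, comorbidities, hemodynamic status"), and the investigator decides.

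Grade 5 (death) is on the severity scale in 4.3.2 but is not named in the grade 4 pathway or in the 3.4 trigger.

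Other routes exist. Under 7.1.5.3.1 a serious adverse event "must be reported to the sponsor by the investigator within 24 hours after the investigator becomes aware of it"; "Each report of a serious adverse event will be reviewed and evaluated by the investigator and the sponsor"; and the investigator must see that the IRB is told. Section 7.1.5.3.2 lists suspension among the actions that may follow a SUSAR. Section 5.11 limits the IDMC to the sample size recommendation.

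**The concern.** A stopping rule should count the hazard it guards against. This one counts a treatment decision taken after the hazard has appeared. Hemodynamic status is a stated factor in that decision, so a patient judged too unstable for a second operation could be managed medically and left out of the count, although that case is among the most serious.

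Two life-threatening toxicity cases managed without removal would be reported and reviewed, but the compulsory pause would not be triggered. Under this protocol, whether enrollment stopped would then be a matter of judgment.

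The hazard is central to this trial. Section 7.1.6 names systemic bupivacaine toxicity as one of two safety areas of interest. Section 1.1 explains that abdominoplasty was chosen partly because it is more vascular than hernia repair, with possible consequences for systemic absorption.

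**Working it through.** **Textual check.** Four steps, each from the protocol:

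1. Is there another compulsory, counted pause? No. The rest of 3.4 is discretionary or is review without a number, and suspension under 7.1.5.3.2 is a possible action, not a required one.
2. Does any grade or finding make removal compulsory? No. Sections 3.1 and 4.3.2 are both permissive.
3. Does it help to read *require removal* as clinical need rather than an operation performed? Not for a surviving patient managed without removal, because 4.3.2 gives that determination to the same investigator. For a patient who dies first, the wording supports either reading.
4. Does another body hold a threshold? Not in this protocol. The IDMC has no safety role.

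**Illustration of size.** The protocol states no operating characteristic for the threshold of 2, so there is no figure of its own to reproduce.

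Inputs:

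- n = 180 INL-001 patients (section 3.2), or 270 if the maximum increase in 9.9 is used: (360 + 180)/2.
- p = 1/612 = 0.001634. Section 1.4.2 reports one LAST-like case and 612 patients given INL-001. The exact (Clopper-Pearson) 95% interval is 0.004% to 0.91%. Using this as a grade 4 or 5 rate is an assumption: the case was ungraded and involved an earlier formulation at 150 mg.
- r = share of cases in which implants are removed. The protocol does not give it, so a range is shown.

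Formula, with independent patients: P(at least 2) = 1 − (1 − q)^n − n·q·(1 − q)^(n−1), where q = p if all cases count and q = p·r if only removals count.

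With n = 180 and p = 1/612:

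- All cases: 1 − 0.7450 − 0.2195 = 0.0355.
- Removals only, r = 0.50 (q = 0.000817): 1 − 0.8632 − 0.1270 = 0.0098.

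| n | p | All cases count | r = 0.75 | r = 0.50 | r = 0.25 |
|---|---|---|---|---|---|
| 180 | 1/612 | 3.6% | 2.1% | 1.0% | 0.3% |
| 180 | 0.91% (upper limit) | 49% | 35% | 20% | 6% |
| 270 | 1/612 | 7.3% | not run | 2.1% | not run |
| 270 | 0.91% (upper limit) | 70% | not run | 35% | not run |

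At r = 1 the two counts are identical.

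One figure needs no event rate. If exactly two such cases occur, the present rule fires with probability r²: 56% at r = 0.75, 25% at r = 0.50 and 6% at r = 0.25.

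**The case against.** The strongest reply is that this is a design choice and not an error. The rule names an event, a number and a consequence, and nothing in the protocol contradicts it. The single LAST-like case on record had its implants removed, so the present rule would have counted it. The proposed trigger also still depends on an investigator's determination. All of this is correct. It limits the point to an inexpensive improvement but does not close the gap, because a rule that counts only removals can stay at zero through repeated grade 4 cases.

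A reader might infer more than the text supports in four respects:

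- *That uncounted cases go unseen.* They do not. The reporting, sponsor review, IRB and SUSAR routes all apply, and the sponsor may stop for safety at any time.
- *That a patient who dies before removal is certainly not counted.* Section 3.4 counts patients who require removal, not those who undergo it. The wording is ambiguous here, not clearly exclusive.
- *That treatment could not be established.* Section 4.3.2 lets the investigator request unblinding after the listed grade 4 events. Section 5.10 adds "Emergency unblinding is allowable if deemed necessary by the investigator, and discussed and agreed with the study medical monitor", and in the case of a SUSAR "unblinding of the sponsor will be performed according to the safety management plan". These routes are discretionary or conditional. Whether severe toxicity would be classed as unexpected depends on reference safety information in the Investigator's Brochure, which is not at hand.
- *That the trial has no threshold anywhere.* The Safety Monitoring Plan (cited in 7.1.2.4) and the safety management plan (cited in 5.10) are not at hand and could contain one.

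**Conclusion.** The point holds, limited to what this protocol fixes: the only compulsory, counted pause rests on a discretionary removal decision. Grade 4 systemic toxicity managed without removal does not advance it, and death before removal is left unclear. The other safeguards are real but carry no mandatory threshold here.

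The textual finding needs no assumptions. Its size cannot be settled from the document. At 1/612 with half of cases removed, the gap is 2.6 percentage points with 180 INL-001 patients (3.55% − 0.98%). The larger gap of about 29 points (48.65% − 19.69%) needs the upper confidence limit and r = 0.50 together, and should not be read as an estimate. This is a cheap improvement; it bears on patient safety and does not affect the efficacy analysis.

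**What to change.** Amend 3.4 so that the pause applies when 2 patients, each counted once, meet either condition:

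- they require implant removal for suspected systemic bupivacaine toxicity (the present trigger, kept); or
- they have investigator-determined systemic bupivacaine toxicity of CTCAE grade 4 or 5, whether or not implants are removed.

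A case counts unless unblinding shows placebo. Treatment is confirmed through the existing routes in 4.3.2 and 5.10 where they apply, and otherwise by someone outside the blinded team. The second condition is added to the first and does not replace it, because it too depends on the investigator's determination. Counting grade 5 explicitly also removes the ambiguity about a patient whose toxicity is fatal before removal.

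Cost: a few sentences and a short unblinding provision, by amendment. No new assessments are needed, because the toxicity event is already recorded under 3.1 and 7.1.6.1 and its CTCAE grade under 7.1.3. The downsides are limited extra unblinding outside the blinded team and a somewhat higher chance of a temporary pause, as illustrated above.
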